#### Grade 3 (QTcF $\geq$ 501 ms)

- Measure electrolyte levels (K+, Ca++, and Mg++) and supply the electrolytes to ensure recovery to the institutional reference ranges.
- Check concomitant drugs, and discontinue drugs that are known to prolong the QT interval, as necessary.
- Interrupt treatment with quizartinib for a maximum of 14 days. Resume treatment with quizartinib at a one-level reduced dose, relative to the dose immediately before the interruption, if the increase in QTcF interval from baseline is 30 ms or shorter or

the QTcF interval recovers to 450 ms or shorter within 14 days after the onset. If Grade 3 QTcF prolongation occurs, subsequent dose increase is not allowed.

Grade 4 (increased QTcF to 501 ms or longer or a 60 ms or longer change in QTcF from baseline associated with any signs or symptoms of TdP, polymorphic ventricular tachycardia, or any other serious arrhythmia)

- Measure electrolyte levels (K+, Ca++, and Mg++) and supply the electrolytes to ensure recovery to the institutional reference ranges.
- Check concomitant drugs, and discontinue drugs that are known to prolong the QT interval, as necessary.
- Discontinue treatment with quizartinib.

#### 9.10.3 Chest X-ray Examination

The date of measurement and the results of investigators' assessment will be recorded in the CRF.

# 9.10.4 MUGA Scan or Echocardiography

The date of measurement and LVEF (%) will be recorded in the CRF.

#### 10. OTHER ASSESSMENTS

Not applicable

#### 11. STATISTICAL METHODS

#### 11.1 General Statistical Considerations

The primary objective (hypothesis) of this study is to confirm that the CRc rate with quizartinib monotherapy is at least 23.5% in Japanese patients with FLT3-ITD positive relapsed or refractory AML.

Efficacy analyses will be performed using the efficacy analysis set. Safety, pharmacokinetic, and biomarker analyses will be performed using the safety analysis set, the pharmacokinetic analysis set, and the biomarker analysis set, respectively.

The analyses, excluding pharmacokinetic and biomarker analyses, in this study will be performed in all patients included in each analysis set regarded as one dose group, whether the dose is increased or reduced.

Unless otherwise noted, continuous variables will be summarized by the number of patients analyzed, arithmetic mean, standard deviation, minimum, median, and maximum,

whereas categorical variables will be summarized by frequency and proportion. Baseline values of each patient, unless otherwise specified, will be the last observed values that are available before the first dose of the study drug. Analyses of changes from baseline (eg, absolute change, shift table) will be performed on patients with baseline values and at least one post-treatment value available.

This study will be conducted using a two-stage design, and interim analysis is planned to be performed once. The details of interim analysis are shown in Section 11.4.

# 11.2 Analysis Sets

The sponsor will finalize the population flag of individual patients for each analysis set after CRF lock. Patients with major Good Clinical Practice (GCP) violations (eg, a violation of the informed consent procedure, a major violation of study procedures) will be excluded from all analysis sets.

- All enrolled patients will include all patients who have signed the ICF.
- All registered patients will include all patients who have signed the ICF and are assessed as eligible for the study.
- The safety analysis set will include all patients who have signed the ICF and received at least one dose of the study drug.
- The efficacy analysis set will include patients who have signed the ICF (including consent for measurement of FLT3-ITD mutations), have a positive result of the FLT3-ITD mutation test performed at Navigate BioPharma, and have received at least one dose of the study drug.
- The pharmacokinetic analysis set will include patients who have signed the ICF and received at least one dose of the study drug, and whose plasma drug concentration data obtained are available for at least one time point after the start of treatment with the study drug.
- The biomarker analysis set will include patients who have signed the ICF and received at least one dose of the study drug, and whose biomarker data shown in Section 6.10 are available for at least one time point after the start of treatment with the study drug.

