## 9.1 Adverse Event Collection and Reporting

All clinical AEs (for the definition, see "9.3.1 Definition of Adverse Events") that occur during the period from the day of the first dose of the study drug to the day of post-treatment observation will be recorded on the AE page of the CRF. SAEs that occur during the period from the day of informed consent to before the first dose of the study drug will also be recorded in the CRF.

Medical conditions (including laboratory values/vital signs that are out of range) that were diagnosed or known to exist prior to informed consent will be recorded as part of complications/medical history.

AEs and SAEs are to be reported according to the procedures in "9.4 Serious Adverse Events Reporting Procedure for Investigators."

All clinical laboratory results, vital signs, and 12-lead ECG results and findings should be appraised by the investigators to determine their clinical significance. Isolated abnormal laboratory results, vital sign findings, or ECG findings (ie, not part of a reported diagnosis) should be reported as AEs if they are symptomatic, lead to study drug discontinuation, dose reduction, require corrective treatment, or constitute an AE in the investigators' clinical judgment.

At each visit, the investigators will determine whether any AEs have occurred by evaluating the patient. AEs may be directly observed, reported spontaneously by the

patient or by questioning the patient at each study visit. Patients should be questioned in a general way, without asking about the occurrence of any specific symptoms. The investigators must assess all AEs to determine seriousness, severity, and causality, in accordance with the definitions in "9.3 Adverse Events." The investigator's assessment must be clearly documented in the site's source documentation.

Always report the diagnosis as the AE or SAE term. When a diagnosis is unavailable, report the primary sign or symptom as the AE or SAE term with additional details included in the narrative until the diagnosis becomes available. If the signs and symptoms are distinct and do not suggest a common diagnosis, report them as individual entries of AE or SAE.

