#### 11.3.3 Safety Analyses

Safety analyses will be performed in the safety analysis set.

AEs that occur or worsen relative to the pre-treatment state after the first dose of the study drug (treatment emergent AEs [TEAEs]) will be tabulated. AEs will be coded using the Medical Dictionary for Regulatory Activities (MedDRA) terminology developed by the ICH, and be tabulated by body organ group using the MedDRA system organ class (SOC) and by AE term using preferred terms (PTs).

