#### 12.3 Data Management

Each subject will be identified in the database by a unique subject identifier as defined by the sponsor.

To ensure the quality of clinical data across all subjects and study centers, a Clinical Data Management review will be performed on subject data according to specifications given to the sponsor. Data will be vetted both electronically and manually for CRFs and the data will be electronically vetted by programmed data rules within the application. Queries generated by rules and raised by reviewers will be generated within the EDC application. During this review, subject data will be checked for consistency, completeness and any apparent discrepancies.

Data received from external sources such as central laboratories will be reconciled to the clinical database in accordance with the data management plan.

SAEs in the clinical database will be reconciled to the safety database.

All AEs and complications/medical history will be coded using MedDRA. Prior and concomitant medications will be coded using the World Health Organization Drug Reference (WHODRUG).

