#### 15.5 Protocol Deviations

The investigator should conduct the study in compliance with the protocol agreed to by the sponsor and, if required, by the regulatory authorities, and which was given approval by the IRBs/ECs.

A deviation to any protocol procedure or waiver of any stated criteria will not be allowed in this study except where necessary to eliminate immediate hazard(s) to the subject.

The sponsor must be notified of all intended or unintended deviations to the protocol (eg, inclusion/exclusion criteria, dosing, missed study visits) on an expedited basis.

The investigator, or person designated by the investigator, should document and explain any deviation from the approved protocol.

If a subject was ineligible or received the incorrect dose or study treatment, and had at least one dose of the study drug, data should be collected for safety purposes. If applicable, the investigator should notify the IRB of deviations from the protocol.

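### Section 11.2 removes patients with major GCP violations from every analysis set, with no exception for safety, so a validly consented, dosed patient can be missing from all safety tables

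*Combined protocol and SAP*

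**What the plan says.** Section 11.2 opens with two general rules and then lists the analysis sets.

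- Timing: "The sponsor will finalize the population flag of individual patients for each analysis set after CRF lock".
- Exclusion: patients with major GCP violations (eg, a "violation of the informed consent procedure, a major violation of study procedures) will be excluded from all analysis sets". The sentence names no exception.
- Safety set, in the list below those rules: "The safety analysis set will include all patients who have signed the ICF and received at least one dose of the study drug".

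Section 11.3.3 then states: "Safety analyses will be performed in the safety analysis set". Section 11.1 says the same. The adverse event, laboratory, vital-sign and ECG summaries (Sections 11.3.3.1 to 11.3.3.4) all draw on this set. The protocol provides no all-treated table and no listing of excluded patients.

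Data capture does not depend on set membership. Under Section 9.1, adverse events from the first dose to the post-treatment observation day "will be recorded on the AE page of the CRF". Section 9.4 requires serious events to be reported within 24 hours. Section 12.3 adds: "SAEs in the clinical database will be reconciled to the safety database". Section 15.5 says that if a subject who was ineligible, or who was given the wrong dose or treatment, had "at least one dose of the study drug, data should be collected for safety purposes".

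**The concern.** The two examples in the exclusion rule differ in kind. Leaving out a patient whose consent was defective is easy to defend. A major procedural violation is different: it can occur in a patient who consented properly and was exposed to the drug, and what happened to that patient is safety information.

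Because the exclusion covers every set, and every safety table uses the safety set, following the rule drops that patient from the whole planned safety summary. The loss is one of tabulation, not of data, but the tables are what the planned safety analysis reports.

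A smaller point concerns efficacy. The trial is open-label (Section 5.1.3) and flags become final only after CRF lock, when responses are known. Consent, dosing and the central FLT3-ITD result are objective criteria. Whether a GCP violation is major is the one judgement in efficacy-set membership.

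**Working it through.** **1. The statements side by side**

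| Patient | Safety-set definition (11.2) | Exclusion rule (11.2) | In the safety tables? |
|---|---|---|---|
| Valid consent, dosed, no major violation | in | not triggered | yes |
| Consent procedure violated, dosed | in, if a form was signed | out | no; defensible |
| Valid consent, dosed, major procedural violation | in | out | the two statements conflict |

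The plan does not say which statement takes precedence. The natural reading is that the exclusion controls, since it comes first and applies to all sets. The third row is the problem.

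**2. Size for safety (illustration)**

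Inputs: 25 and 41 are the Stage 1 and total efficacy-set sizes (Section 11.5). I assume that the same numbers are dosed; the safety set could be larger, because it does not require a positive central FLT3-ITD result. I also assume one exclusion.

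With x events among n dosed patients, the rate x/n becomes (x − 1)/(n − 1) if the excluded patient had the event, and x/(n − 1) if not.

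| Full set | Excluded patient had the event | Excluded patient did not |
|---|---|---|
| 1/25 = 4.0% | 0/24 = 0% | 1/24 = 4.2% |
| 2/25 = 8.0% | 1/24 = 4.2% | 2/24 = 8.3% |
| 1/41 = 2.4% | 0/40 = 0% | 1/40 = 2.5% |
| 2/41 = 4.9% | 1/40 = 2.5% | 2/40 = 5.0% |

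Exact (Clopper-Pearson) 95% intervals: 1/25 gives 0.1% to 20.4%, and 0/24 gives 0% to 14.2%; 1/41 gives 0.06% to 12.9%, and 0/40 gives 0% to 8.8%. The rate can move either way.

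**3. The efficacy clarification**

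The plan's own figures come first. With X1 ~ Bin(25, p) and X2 ~ Bin(16, p), the chance of declaring efficacy is

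P(X1 ≥ 11) + Σ (x = 4 to 10) P(X1 = x) · P(X2 ≥ 15 − x).

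This gives 0.0482 at p = 23.5% and 0.8137 at p = 42%, matching the 0.048 and 0.814 in Section 11.5.

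- *Exclusion unrelated to response, replaced by the next registered patient:* both figures are unchanged.
- *Exclusion unrelated to response, not replaced, threshold kept at 15:* 0.0411 and 0.7813 if a Stage 2 member is lost; 0.0420 and 0.7855 if a Stage 1 member is lost after the interim decision. Type I error falls, and power drops by about 3 percentage points (0.8137 − 0.7813 = 0.0324; 0.8137 − 0.7855 = 0.0282).
- *Worst case:* the count is exactly 14 of 41, a non-responder is excluded because of that, and a surplus patient takes the place. At p = 23.5% the chance of reaching the final look with exactly 14 is 0.0362. The added error is 0.0362 × 0.235 = 0.0085, and the total is 0.0482 + 0.0085 = 0.0567.

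The second and third cases need opposite conditions (no replacement, or a surplus patient), so they cannot be added together.

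**The case against.** **The trigger may be narrow.** The rule concerns major GCP violations, and Section 15.8 lists a major GCP violation and a significant protocol deviation as alternatives. Not every serious procedural lapse need count. Nothing in the text reviewed defines the term, and the separate SAP named in Section 11.6 may do so. This stands and lowers confidence. It does not remove the conflict, because Section 11.2 itself gives a procedural violation as an example.

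**Section 15.5 does not settle the matter.** A reader might infer that Section 11.2 discards exactly the data that Section 15.5 says to collect. The documents do not support that. Section 15.5 covers ineligible or wrongly treated patients and does not call them major GCP violators. It helps the argument only where the two groups overlap.

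**The data are not lost.** Correct: CRF entry, 24-hour reporting and reconciliation are unaffected. A reader might infer that safety events go unreported, or that the exclusion makes the drug look safer. Neither follows. The loss is from the tables, and the direction is unknown.

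**The efficacy point is mostly handled.** A reader might infer that late flags inflate type I error to 0.057. That figure requires an exclusion driven by response and a surplus patient, and nothing in the documents suggests the former. If the worst case arose in 10% of trials ending at 14 of 41, type I error would be 0.0482 + 0.1 × 0.0085 = 0.0491. It passes 0.05 only above (0.05 − 0.0482)/0.0085, about 21%. Section 11.4 enrols to a count of set members, Section 11.4.3 takes them in registration order, and Section 11.6 fixes the SAP before database lock. Leaving major violators out of the primary efficacy set is a choice the sponsor may reasonably make. What stands is a request for clarification.

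**Conclusion.** The safety point holds. As written, Section 11.2 allows a validly consented, dosed patient to be missing from every safety table, and it contradicts its own definition of the safety set. This follows from the text and rests on no assumed figure. The size is illustrative: with 25 dosed, one exclusion can turn 1/25 into 0/24. The documents give neither an expected number of exclusions nor a direction of bias.

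The efficacy point is secondary and conditional. The stated error rate and power are correct for exactly 25 and 41 members. The documents give no sign of response-driven exclusion, and 0.057 is a worst case that should not be quoted as an expected error rate.

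Overall confidence is medium, because the separate SAP was not in the text reviewed and may define a major violation or exempt the safety set. The point should be fixed, but it does not threaten the trial's conclusion.

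**What to change.** 1. In Section 11.2, limit the GCP exclusion so that the safety analysis set keeps every patient with valid consent and at least one dose. Identify patients with major violations in a listing.
2. As a clarification, state that any GCP exclusion from the efficacy set is decided and documented on grounds unrelated to response, before the CRc count is tabulated at the interim and at the final analysis. It cannot simply be tied to the data cut-off, because Section 11.4.3 derives that date from each patient's response.

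The cost is a change of wording in Section 11.2, carried into the SAP. Sample size and decision thresholds stay the same. The downside is that the safety tables will include some data from patients with procedural violations, which the listing makes visible.

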#### 11.3 Statistical Analyses

# 11.3.1 Efficacy Analyses

Efficacy analyses will be performed in the efficacy analysis set.

#### 11.3.1.1 Primary Efficacy Analyses

For the CRc rate, frequency tables will be prepared, and the 90% and 95% confidence intervals (CIs) will be calculated.

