Registration of patients will be continued during the course of the interim analysis. If it is decided to terminate the study early, the registration of patients will be discontinued; however, treatment with the study drug in patients who continue receiving the study drug will be continued until "5.7.1 Discontinuation Criteria for Treatment with the Study Drug" are met.

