# 7.2 Best Response

Best response is defined as the best measured response over all response assessments (CR, CRp, CRi, PR, NR, or Unknown) at all time points after the first dose of the study drug. The best response is presented as CR, CRp, CRi, PR, NR, or Unknown in descending order of efficacy.

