#### 11.4 Interim Analysis

This study is planned with a two-stage design; in Stage 1, interim analysis will be performed when 25 patients are included in the efficacy analysis set. If it is decided to continue the study based on the interim analysis (for the assessment criteria, see "11.4.3 Criteria"), registration of patients will be continued until 41 patients are included in the efficacy analysis set (16 patients in Stage 2). Registration of patients will be continued during the course of the interim analysis.

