#### 11.4.3 Criteria

The assessment criteria in Stage 1 (25 patients will be chosen from the efficacy analysis set in the order of registration) and at the end of Stage 2 (41 patients will be chosen from the efficacy analysis set in the order of registration) are shown below. Concerning patients for whom the study is continued as of the data cut-off date (see below) of the interim analysis, the best response will be calculated from the data collected up to the data cut-off date, and whether CRc is achieved or not will be assessed.

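### Does the plan need changing because the 90% CI for the CRc rate may rest on more patients than the efficacy decision?

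*Combined protocol and SAP*

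**What the plan says.** The decision rule is in section 11.4.3. At Stage 1, "25 patients will be chosen from the efficacy analysis set in the order of registration"; at the end of Stage 2, "41 patients will be chosen from the efficacy analysis set in the order of registration". For patients still on study, "the best response will be calculated from the data collected up to the data cut-off date". The cut-off is the latest, over the decision patients, of each patient's first date of CRc, discontinuation or Day 1 of Cycle 4. The section applies the same procedure to the analysis at the end of Stage 2. Efficacy is declared at 11 or more of 25, or at 15 or more of 41; futility is declared at 3 or fewer of 25.

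Estimation is in section 11.3. Section 11.3.1 says "Efficacy analyses will be performed in the efficacy analysis set", and section 11.3.1.1 adds that "the 90% and 95% confidence intervals (CIs) will be calculated". Neither mentions the first 25 or 41 patients, the cut-off or an interval method. Section 11.2 defines the set as consented, dosed patients with a positive central FLT3-ITD test, with no cap on number. Section 7.2 defines best response over assessments "at all time points after the first dose of the study drug".

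On recruitment, section 3.1 says "Registration of patients will be continued during the course of the interim analysis". Section 11.4 says that, if the trial goes on, "registration of patients will be continued until 41 patients are included in the efficacy analysis set". Section 11.6 leaves detailed methods to a separate statistical analysis plan (SAP), which is not part of the text at hand.

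**The concern.** A two-sided 90% interval is the natural companion to a one-sided 5% test, so readers will compare its lower limit with 23.5%. That comparison is only sure to match the decision if both use the same patients and the same data.

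The plan allows them to differ in two ways. First, recruitment is not paused for the interim, so the set may already exceed 25 when an efficacy stop is called. It could also pass 41 slightly, because section 6.1 lets patients be assessed for eligibility before the central FLT3-ITD result. Second, a first remission after the cut-off counts under section 7.2 but not under section 11.4.3.

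A trial declared effective could then report an interval that includes 23.5%, or a trial that missed its boundary could report one that excludes it. With no interval method named, a borderline reading could also turn on a later choice of method.

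**Working it through.** **Inputs.** Threshold 23.5%, expected rate 42%, one-sided 5% level (section 11.5); boundaries from section 11.4.3. The number of extra patients, m, and the interval method are not in the plan and are assumptions here.

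**1. The plan's own figures.** With X1 ~ Bin(25, p):

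P(effective) = P(X1 ≥ 11) + Σ(x = 4 to 10) P(X1 = x) · P(Bin(16, p) ≥ 15 − x)

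| p | Futility stop | Efficacy stop | Effective overall |
|---|---|---|---|
| 23.5% | 0.1280 | 0.0190 | 0.0482 |
| 42% | 0.0013 | 0.4956 | 0.8137 |

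These round to the table in section 11.5. Expected N at 42% is 25 + 16 × (1 − 0.0013 − 0.4956) = 33.05, against 33.0 stated. No confidence interval enters any of these quantities.

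**2. Same patients, same data.** Clopper-Pearson 90% lower limit L(x, n) = the 5th percentile of Beta(x, n − x + 1):

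- 11/25: 27.0%, effective, above 23.5%.
- 15/41: 24.1%, effective, above 23.5%.
- 14/41: 22.0%, not effective, below 23.5%.

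L rises with x, so agreement at the boundaries means agreement at every final outcome. Wilson (25.4% at 15/41, 23.3% at 14/41) and Wald (24.2%, 22.0%) agree too, as does mid-P. The result 10/25 gives 23.56%, but that outcome continues to Stage 2 and is not a final decision.

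**3. Extra patients after a Stage 1 efficacy stop.** The worst case is 11/25 followed by m non-responders: 11/28 gives 23.8%, still above the threshold, and 11/29 gives 22.9%. So m = 1 to 3 cannot produce a conflict. For m = 4 the conflict needs exactly 11/25 and then four non-responders:

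P(X1 = 11 | 42%) × 0.58⁴ = 0.156 × 0.113 = 0.0176

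Over m = 4 to 12, the share of all trials lies between 0.6% (m = 6) and 2.4% (m = 7).

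**4. Extra patients at the end of Stage 2.** At 42%, a trial ends at exactly 15/41 with probability 0.0815 and at exactly 14/41 with probability 0.0697.

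- m = 1: 15/42 gives 23.47%, so conflict needs 15/41 and one non-responder: 0.0815 × 0.58 = 0.047.
- m = 2: 15/43 gives 22.9% and 16/43 gives 24.9%. Conflict is 0.0815 × 0.58² + 0.0697 × 0.42² = 0.0274 + 0.0123 = 0.040.
- m = 3: 0.046. m = 4: 0.060.

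The range is therefore 4.0% to 6.0% of all trials, given that m extra patients are present in every trial reaching this point. At m = 0 it is zero. Method matters only when m > 0: at 15/42 Clopper-Pearson gives 23.47%, Wald 23.55% and Wilson 24.8%.

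**5. Late responses.** One first remission after the cut-off turns 14/41 (22.0%) into 15/41 (24.1%). About 7.0% of trials end at 14/41 at a true 42%. That is an upper bound on this route, not its rate, because the plan gives no frequency of remissions first seen that late.

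**The case for a change.** The strongest case for a change is that the plan settles which patients count for the decision and leaves the same question open for the estimate. Choosing 25 or 41 patients from the set already allows for a larger set, so the authors foresaw extra patients. The trial is open-label, an in-house committee sees the interim data, and section 11.6 requires the SAP to be fixed only before database lock. Population, data date and interval method could therefore be chosen with responses in view. A few sentences would close the gap.

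Part of this stands. Section 11.3.1.1 lacks a cross-reference, and nothing says which estimate leads after a Stage 1 efficacy stop. The rest carries less weight:

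- The counts in section 11.4.3 are fixed in advance, so a late choice of interval cannot turn a failed trial into a successful one.
- Section 11.4.3 already carries its cut-off procedure to the end of Stage 2. That text sits among the decision criteria, so it does not settle the point for section 11.3.1.1, but it makes the intended reading fairly clear.
- The unnamed method creates no conflict by itself, since the four methods tried all agree with the rule on 25 or 41 patients.
- Estimating the rate in every dosed, centrally confirmed patient is legitimate and uses more data. After an efficacy stop at a true 42%, the mean estimate on the 25 is 50.0%; with eight more patients it is (25 × 50.0% + 8 × 42%) / 33 = 48.1%. Putting the 25-patient estimate first would make the overstatement slightly larger.

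**Conclusion.** The mismatch is real on paper, but it is a gap in reporting detail and calls for no change to the plan. Followed as written, the plan gives a sound decision with the stated error rates, together with a legitimate estimate in the full efficacy analysis set.

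The best-supported route to a conflict is recruitment during the interim. It produces none with up to three extra patients and at most 2.4% with four to twelve (Clopper-Pearson, true rate 42%). The larger Stage 2 figures rest on an overrun past 41 that the plan does not intend and for which it gives no number. No rate can be put on late responses.

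An analyst completing the SAP would ordinarily name the interval method, state the data date, and show the decision patients beside the full set if the two differ. A reader who met a discrepancy could resolve it from section 11.4.3, where the counts govern. The conclusion assumes that the decision is reported from those counts, as that section requires.
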